7.2. HANDLING DEPENDENT OBSERVATIONS

Due to the design of the OLE, a participant may have received treatment in a crossover nature. For those participants, special data handling methods are required. For the passive-active group, assessments will be assigned to the treatment received at the time of the given assessment. All observations captured up to the first treatment with active tvCVS will be assigned to the passive treatment. All observations at or after the first treatment with active tvCVS will be assigned to the active treatment.

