4.1 Study Schedule and Activities

The STEM-PD RCT will last 113 days (plus additional visit window days), beginning with a pre-treatment baseline period of four weeks (28 days). The baseline period will be followed by the treatment period of 12 weeks (84 days). During the RCT, clinical assessments will occur every 4 weeks (28 days) and efficacy will be determined by evaluating therapeutic gains at the end of 12-week (84 day) treatment period relative to the average of the baseline.

Upon completion of the STEM-PD RCT, participants will be offered the opportunity to participate in the open label extension (OLE) phase (to commence immediately upon completion of STEM-PD RCT) which will last 36 weeks (252 days). In the OLE, all study participants will receive active treatment for 12 weeks (84 days) followed by a 16-week (112 day) post treatment observation period and then an additional 8-week (56 day) treatment period. See Schema for

details.

The phases and activities of the study are listed below:

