4.1.1 STEM-PD RCT

Pre-screening procedures: Sites will recruit potential participants from their practice/service or the general public as long as inclusion/exclusion criteria can be verified. The use of advertisements may be used at the site's discretion. During the pre-screening period, the study should be described, preliminary questions answered, and review of potential participant's medical records can occur, however, no protocol-specific activities should occur until after informed consent is obtained and documented.

Study screening procedures (Day –14 to –1):

Informed Consent

Participants will be shown an example of the Study Device as part of the informed consent process. Potential participants should be given a private space to review the ICF and an ample opportunity to have all questions answered. Capacity to provide consent must be assessed by a clinician with experience working with Parkinson's Disease patients, and should be documented, as no Legally Authorized Representative is allowed. Informed consent should be signed and dated by both the study participant and authorized study staff performing the informed consent process, and a signed and dated copy provided to the participant, prior to any study related activities being conducted. Although participants will only consent at the screen for involvement in the 16-week (112 days) STEM-PD RCT portion of the study, screening applicants who do not anticipate participating in the 36-week (252 days) OLE will be excluded from the study.

Additionally, the protocol-required study partner will also be provided with an informed consent to review and discuss. The purpose of the informed consent for the study partner is to ensure that they understand and agree that they are required to assist, if necessary, the participant in the execution of certain at home assessments, such as the TUG, as well as answer specific questions by the study staff related to the participant's overall health and activities of daily living. The study partner should be afforded the same informed consent process stipulations as the participant, including that the informed consent be signed and dated by both the study partner and the authorized research study staff performing the informed consent process, and provided a sign and dated copy.

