Randomization will occur only after all scheduled assessments and activities have been completed and normal findings on the ear exam is verified and will occur by selecting an envelope from the randomization package, scanning the bar code to the Device and ensuring that the treatments are loaded. The participant and study partner will be trained on how to use and care for the Device, take it home and commence with twice daily treatments.

Clinician version – not for patient use

Treatment Period: The 12 weeks (84 days +/- 3 days) following the pre-treatment baseline period constitute the treatment period. Participants will self-administer treatments twice daily for the full treatment period up until the scheduled end of treatment visit. Treatment adherence will be recorded by the device.

Study staff will confirm and document that they remain blinded to treatment allocation at the beginning of every study visit after randomization. If a study staff member directly responsible for assessment or safety evaluation becomes unblinded, they will no longer be eligible to complete the delegated study assessments per the protocol for that participant.

Phone contacts: (days 43, 56, 71, 84, 99, 112: +/- 1 day)

Participants will complete interim assessments at weeks 8 (day 56) and 12 (day 84). During phone calls scheduled every 2 weeks, study staff will review concomitant medications, potential adverse events and device treatment adherence and issues with the study participant. Study sites are encouraged to have continuous communication with the study participant and study partner outside of the defined protocol visits, in the manner most accommodating to them, to assist with rapport, retention, and the identification of medication changes or adverse events in real-time.

- Interim assessments (week 8/days 56, 57 and week 12/days 84, 85)
 - i. ePROs (days 56 and 84 +/- 1 day) – to be completed in the on-state
 - PDQ-39
 - MDS-UPDRS Part II
 - Transition Questionnaire (day 56 only)
 - ii. Treatment Virtual visits 1 and 2 (days 57 and 85 +/- 3 days)
 - Concomitant medication and adverse event review
 - MDS-NMS (does not include the NMF subscale)
 - Modified MDS-UPDRS Part III (excluding items related to rigidity and postural reflexes)

Virtual visits will be performed using the site's standard of care telemedicine platform.
- End of treatment visit (week 16/days 112, 113 or early termination)
 - i. ePROs (day 112 +/- 1 day) – to be completed in the on-state
 - PDQ-39

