8.1 Device Deficiency

A device deficiency is an inadequacy of a medical device related to its identity, quality, durability, reliability, safety, or performance, such as malfunction, misuse or use error and inadequate labeling.

All device deficiencies will be documented, and the device will be returned to the device manufacturer for analysis, if possible. Device deficiencies are NOT to be reported as AEs. However, if there is an AE that results from a device deficiency, that specific event would be recorded on the appropriate CRF.

8.2 Adverse Events (AEs), Adverse Device Effects (ADEs), Serious AEs (SAEs), Serious Adverse Device Effects (SADEs), Unanticipated Adverse Device Effects (UADE) and Unanticipated Problem Reporting

8.2.1 AEs, ADEs, SAEs, SADEs and UADEs will be defined per ISO14155:2020 and/or 21 CFR Part 812, as described below.8.2.1 Adverse Event (AE):

An AE is any untoward medical occurrence, unintended disease or injury, or untoward clinical signs (including abnormal laboratory findings) in participants, users, or other persons, whether or not related to the investigational medical device. This definition includes events related to the investigational medical device and the events related to the procedures involved. For users and other persons, this definition is restricted to events related to the investigational device. AEs will be collected starting from the time the participant signs informed consent until the follow-up period is completed.

8.2.2 Adverse Device Effect (ADE):

An Adverse Device Effect (ADE) is an AE related to the use of an investigational medical device. This definition includes AEs resulting from insufficient or inadequate instructions for use, deployment, implantation, installation, or operation, or any malfunction of the investigational medical device. This definition includes any event resulting from use error or from intentional misuse of the investigational medical device.

Traditional, diagnostic CVS has been used for roughly a century, and there are no reports in literature of significant adverse events.

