7.9. SAFETY ANALYSIS

7.9.1. Adverse Events (AEs)

Participants will be assessed for AEs every two weeks at minimum (either at study visits or during phone calls). For each group, the AEs will be summarized with frequency and percentage by preferred (PT) term, with all participants in that treatment group as the denominator. Classification will utilize MedDRA System Organ Class (SOC) based on MedDRA® Version 26.0 or other terminology/classification common to Parkinson's disease (e.g., falls, freezing of gait, etc.). AE incidence will be summarized by both severity and causal relationship to Device treatment (as determined by the blinded Principal Investigator or designated study personnel). AEs deemed to be of "possible" or "probable" relationship or "related" to the Device will also be considered as device related. AEs that occurred during the baseline period and post randomization will also be summarized. Additionally, the number of events and number of device-related events per person will be reported as a distribution.

The AE summary tables will provide an overall summary of AEs including the number and percentage of participants who experienced any AE, any SAE, any ADE, any SADE, any UADE, and any discontinuations in study participation due to an AE.

The objectives for the adverse event analysis in this study will be to confirm the safety/tolerability of tvCVS for the treatment of PD. For this, AE rates will be evaluated in the passive-active cohort. McNemar's test will be used to compare AE rates with tvCVS treatment during the first 12-week treatment period of the OLE as compared to AE rates during the passive treatment period in the RCT. Examination of the safety/tolerability of treatment periods longer than 12-weeks, will be evaluated as part of the procedures described within the appendices to this SAP.

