7.3. DEFINITIONS

Study day: The study day will be calculated in reference to the date of the first baseline virtual visit (Day 0) of the study.

Baseline value: Where multiple data points are collected during the baseline period, the baseline value for each participant will be calculated as the mean of assessments taken during the baseline period excluding the screening value unless otherwise noted. Exceptions to this will be for the following outcomes:

- PRO-PD where the baseline value is defined as the second data collection (i.e., first data collection will be discarded), if both are available, otherwise the first data point will be used (this value could be the Screening value). The scale's author indicated that scores from the first completion of the assessment have higher variability relative to the scores from subsequent administrations.
- the MDS-UPDRS III where the baseline value is defined as the second data collection (i.e., the in-clinic assessment). However, if the end of treatment visit is collected virtually due to the inability of the participant to attend the in-clinic visit, the data from the first virtual baseline assessment, appropriately prorated, will serve as the baseline for that participant.

To be considered baseline data, data must be collected prior to or on the day of first treatment with the study Device.

Duration of Follow-up: The duration of follow-up will be defined as the number of days from Baseline Visit 1 until the End of Study assessment or the last completed visit (phone call, virtual or in clinic).

Adverse Event:

Per protocol, an AE is any untoward medical occurrence, unintended disease or injury, or untoward clinical signs (including abnormal laboratory findings) in participants, users, or other persons, whether or not related to the investigational medical device. This definition includes events related to the investigational medical device and the events related to the procedures involved. For purposes of analyses, any AE specified on the Adverse Events eCRF page is considered an AE.

Adverse Device Effect (ADE):

Per protocol, an ADE is an AE related to the use of an investigational medical device. For purposes of analysis, any AE specified on the Adverse Events eCRF page that is possibly related, probably related, or related to the study device will be considered an ADE.

Serious Adverse Event (SAE):

Per protocol, a SAE is an AE that has

- Led to death,

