7.8. SAFETY ANALYSIS

7.8.1. Adverse Events (AEs)

Participants will be assessed for AEs every two weeks at minimum (either at study visits or during phone calls). For each group, the AEs will be summarized with frequency and percentage by preferred (PT) term, with all participants in that treatment group as the denominator. Classification will utilize MedDRA System Organ Class (SOC) based on MedDRA® Version 26.0 or other terminology/classification common to Parkinson's disease (e.g., falls, freezing of gait, etc.). AE incidence will be summarized by both severity and causal relationship to Device treatment (as determined by the blinded Principal Investigator or designated study personnel). AEs deemed to be of "possible" or "probable" relationship or "related" to the Device will also be considered as device related. AEs that occurred during the baseline period and post randomization will also be summarized. Additionally, the number of events and number of device-related events per person will be reported as a distribution.

The AE summary tables will provide an overall summary of AEs including the number and percentage of participants who experienced any AE, any SAE, any ADE, any SADE, any UADE, and any discontinuations in study participation due to an AE. Differences between the two arms for each AE type will be evaluated by a Fisher's exact test.

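### Neither SAP limits its adverse-event tests to events that start after device use: the RCT arm comparison is diluted, and two OLE rules conflict on what counts as passive

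*SAP*

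**What the plan says.** **Collection.** Protocol section 8.2.1: "AEs will be collected starting from the time the participant signs informed consent until the follow-up period is completed". Consent is taken at screening, between day -14 and day -1 (Protocol 4.1.1). Randomisation is at the day 29 visit, and the first treatment is taken at home afterwards (Protocol 6.3). On the treatment period, Protocol 4.1.1 says: "The 12 weeks (84 days +/- 3 days) following the pre-treatment baseline period constitute the treatment period".

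**RCT SAP (Appendix 1 to the OLE SAP).** For analysis, section 7.3 states that "any AE specified on the Adverse Events eCRF page is considered an AE". Section 7.8.1 sets out tables of participants with any AE, SAE, ADE, SADE or UADE and then adds: "Differences between the two arms for each AE type will be evaluated by a Fisher's exact test". No onset window is given. The section also asks for a summary of baseline-period and post-randomisation AEs, but does not say that the test uses only the latter.

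**OLE SAP.** Section 7.2, on the group that crosses from passive to active, states: "All observations captured up to the first treatment with active tvCVS will be assigned to the passive treatment". The sentence before it assigns assessments by the treatment being received at the time. Section 7.9.1 specifies McNemar's test of the first 12-week OLE treatment period against "AE rates during the passive treatment period in the RCT". Section 7.8.2, on the primary endpoint, gives the RCT treatment period as days 29-113.

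**The concern.** AE frequency is a named safety endpoint in the protocol and in both SAPs. An event that starts before anyone has used the device carries no information about the device.

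In the RCT such events fall on both arms alike. They fill up the any-AE and SAE categories: a participant who already has a baseline event counts as having an AE whatever happens later. A real excess on active treatment then becomes harder to see.

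In the OLE the comparison is within person and the two windows are set by rule. If the passive window also took in screening and baseline, it would be longer than the active window. A longer window collects more events, so the error would run in one direction only, towards active treatment looking safer. The two OLE sections lead to different windows, and nothing says which prevails for AEs.

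**Working it through.** **Inputs from the documents**

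- Pre-device days: from day -14 to day 29 = 14 + 29 = 43 at most. Counting from day 0 only = 29. Visit windows of +/- 3 days are ignored.
- Treated days per period: 84.
- RCT: 184 randomised at 1:1 = 92 per arm. OLE passive-active group: 74 expected (83 x 0.9 = 74.7).
- Two-sided alpha of 0.05 (section 7.1 of each SAP).

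**Assumptions, since the documents give no AE rates.** The background hazard is constant. The background risk of at least one AE in 84 days, p, is 20% to 60%. The hazard on active is multiplied by a rate ratio of 1.5 or 2.

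**The plan's own figure.** The SAP gives no power for any AE test. Its stated 89.2% for the 83-per-arm comparison on MDS-UPDRS Part I reproduces: 2.64 / (5.32 x sqrt(2/83)) = 3.197, and Phi(3.197 - 1.960) = 0.892.

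**RCT.** With d pre-device days counted and rate ratio r:

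- passive: 1 - (1-p)^((84+d)/84)
- active: 1 - (1-p)^((84r+d)/84)

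Example with p = 30%, r = 2, d = 43: passive 1 - 0.7^1.512 = 41.7%, active 1 - 0.7^2.512 = 59.2%. The difference is 17.5 points, against 51.0 - 30.0 = 21.0 points for treated days only.

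The table gives passive v active risk, then the power of the Fisher test to show active worse (exact enumeration, 92 per arm, r = 2):

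| Background risk | Treated days only | Plus 29 days | Plus 43 days |
|---|---|---|---|
| 20% | 20.0 v 36.0: 62% | 25.9 v 40.7: 51% | 28.6 v 42.9: 47% |
| 30% | 30.0 v 51.0: 79% | 38.1 v 56.7: 65% | 41.7 v 59.2: 60% |
| 50% | 50.0 v 75.0: 93% | 60.6 v 80.3: 80% | 64.9 v 82.5: 73% |

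With r = 1.5 and p = 30%, the difference falls from 11.4 to 10.1 points (29 days) or 9.5 points (43 days), and power from 32% to 23% or 20%. With r = 1, the chance of a significant result against active stays at 1.6% to 1.8% in every window.

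**OLE, conditional on section 7.2 being applied to AEs.** The passive window would be up to 43 + 84 = 127 days, or 29 + 84 = 113 days from day 0. The ratios to 84 are 1.51 and 1.35. At p = 30% with no device effect, the expected risks over the 127- and 84-day windows are 1 - 0.7^1.51 = 41.7% passive against 30.0% active. A true 1.51-fold rise on active would give equal proportions.

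Simulated exact McNemar test (74 pairs, 20,000 runs, periods independent within a person):

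| Background risk | Power to show active worse, r = 2: 84 / 113 / 127 passive days | False finding for active, r = 1: 84 / 113 / 127 passive days |
|---|---|---|
| 20% | 50% / 20% / 11% | 1.6% / 9.6% / 17.3% |
| 30% | 68% / 29% / 16% | 1.7% / 13.0% / 25.7% |
| 50% | 85% / 39% / 21% | 1.7% / 20.4% / 38.5% |

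At 60% background risk the last figure reaches 41%. When AE proneness varies between people (gamma frailty, variance 1, p = 30% setting), the pattern holds: power at r = 2 falls from 54% to 11%, and the false finding rises from 1.5% to 19%, going from 84 to 127 passive days.

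**The case against.** **OLE.** The section that specifies the AE test is 7.9.1, and it names the passive treatment period. Section 7.8.2 and the protocol both place that period after baseline. Section 7.2 does not mention AEs, and its preceding sentence assigns by treatment received, which before day 29 is none. This is a strong argument. A reader might infer from section 7.2 that pre-device AEs will be counted as passive and will mask harm. The documents do not support that as settled, because the more specific text points to 84 days against 84. What remains is a conflict: section 7.2 is unbounded, covers all observations in the very group that is tested, and is not overridden by section 7.9.1.

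**RCT.** The SAP never says outright that the Fisher tests count everything since consent, and the baseline and post-randomisation summaries will let a reader separate the counts. That is fair, but the stated AE definition has no time limit and no sentence narrows the test. A reader might also infer a biased arm comparison. That does not follow, because pre-randomisation events are balanced in expectation and the null rejection rate is unchanged.

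**Device-related harm.** Both SAPs define ADE and SADE by relation to the device, and UADE by its designation on the SADE/UADE report form. An event before device use should not be rated as related, so those comparisons are essentially untouched. A claim that device-related events in general are masked would go too far.

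**Weight.** No success criterion depends on these p-values, and the AE tests were never powered. This lowers the severity but leaves the gap in place.

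**Conclusion.** The point holds as a moderate one. In the RCT, the AE rules as written let events from up to 43 device-free days into the any-AE, SAE and preferred-term counts. The effect is dilution without directional bias: for a doubled AE hazard, a loss of about 15 to 20 percentage points of power with 43 days, or 11 to 14 with 29 days, at 20% to 50% background risk.

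In the OLE, sections 7.2 and 7.9.1 need to be reconciled. The 127-against-84-day distortion is what would follow if the unbounded rule were applied to AEs; it is not the established plan.

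The window lengths come from the documents. The AE risks, rate ratios and constant hazard are assumptions, so the power figures show scale only.

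**What to change.** 1. In both SAPs, define a treatment-emergent AE for each period: onset, or worsening, on or after the first device treatment of that period.
2. RCT SAP 7.8.1: run the Fisher tests on AEs that are treatment-emergent from the first RCT treatment to the end-of-treatment visit.
3. OLE SAP 7.2: state that AEs before the first passive treatment belong to neither condition. McNemar's test in 7.9.1 then compares about days 29-113 with days 113-197.
4. Report pre-device AEs in a separate table or listing.

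The cost is SAP wording and one derived flag per period. The device already logs the date of every treatment (Protocol 6.4). AE onset dates are assumed to be on the case report form, as the planned split into baseline and post-randomisation AEs implies. No clinical procedure changes. The downside is that the tested counts will be lower than the all-AE listing, which a footnote can explain.

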7.3. ANALYSIS POPULATIONS

Intent-to-treat Population (ITT): All eligible participants who are allocated a device in the RCT and receive one treatment in the OLE will be included in the primary analysis of efficacy and safety.

Modified Intent to treat (mITT): All eligible participants who have completed at least one treatment with the study device allocated during the OLE and have completed at least one assessment during the OLE will be included in the mITT analysis. This will be considered a secondary analysis to supplement the findings of the primary analysis and will only be performed for endpoints for which regularly scheduled post-treatment data exists.

Per-protocol Population (PP): All eligible participants who (1) who demonstrate at least 70% treatment adherence with the Study Device during the first 12-week OLE treatment period, (2) have completed the regularly scheduled end of treatment period 1 visit (day 197), (3) have not had changes to medications used to treat motor and/or non-motor symptoms of PD between the baseline 1 (day 0) and OLE end of treatment period 1 visit (day 197) and (4) have not had changes

to medications that mimic motor and/or non-motor symptoms of PD between the baseline 1 (day 0) and OLE end of treatment period 1 visit (day 197) will be included in the PP analysis. This will be considered a secondary analysis to supplement the findings of the primary analysis and key secondary analyses.

